8.4 Clinical Management of Adverse Events

By definition, an adverse event can be either new finding or symptom or a worsening of a preexisting condition. In order to accurately capture adverse events in follow-up, a thorough baseline history will be obtained at Visit 1. For example, for participants who endorse a history of headache, site staff will probe for and record details surrounding the condition such as frequency, location, duration, medication use, triggers, etc. Only by eliciting a full description will study staff be equipped to determine whether a subsequent event in follow-up is a clinically distinct event or not. Adverse events will be elicited at each follow-up visit. Referral to appropriate care will be offered to participants as needed.

Any Grade 3 AE's that are deemed to be related to the study product will be reviewed within 5 days by an ENT investigator. The ENT investigator and the PI will determine whether the participant will continue in the study.

If a participant experiences a Grade 4 AE related to the study product or any SAE related to the study product, the study product will be held. The AE will be reviewed by the ENT investigator within 3 days. They will be discontinued from the study and followed for safety and outcome of the event.

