7.5 Visit 4 [Extended Dosing; 1st week of study product provision]

Visit 4 will occur 5-49 days after Visit 3. If any of the safety labs (e.g.Hemoglobin, AST, ALT, Creatinine, bilirubin) obtained at Visit 3 are returned as Grade 2 or higher, this visit will be postponed until the abnormal lab returns to Grade 1 or Grade 0 but within the 49-day window period.

Ideally, participants will return within the week for Visit 4 but the extended window will allow for flexibility for the participant or any disruptions to visit scheduling caused by external forces, for example a spike in SARS-CoV-2 cases at the institution prompting a pause in study visits. Medical history will be updated, a targeted physical exam conducted, safety labs, blood and respiratory sampling obtained, and study product provided to the participant. After reviewing administration instructions with the participant, the first dose of the 13-day course will be self-administered under direct observation in the clinic. The participant will then self-administer product daily at home for the remainder of the dosing period. A one-week supply will be provided at Visit 4.

Participants will be provided with an administration log to record date and time of drug

administration.

Table 4:	Visit 4	Follow-up	Visit	Procedures
		i onon ap	1010	110000000000

VISIT 4 FOLLOW-UP VISIT [week one of extended dosing]				
Component	Procedure/Analysis			

ADMINISTRATIVE	 Collect/Update Contact Information Visit Questionnaire Quality of Life Survey (pre-dose) Update Medical History and Concomitant Medications Protocol Counseling Provision of Study Product (week one supply) Assess/Document Adverse Events Schedule Next Study Visit Participant Reimbursement 				
	CBC with platelets				
BLOOD					
	AOI, ALI Creatinine				
	Total Bilirubin				
URINE	 Pregnancy test (participants of childbearing potential) 				
OROPHARYNGEAL	Q-GRFT level				
NASAL	Q-GRFT level				
NASOPHARYNGEAL	Q-GRFT level				
	Targeted Physical Exam				
PHYSICAL EXAM	Assessment of Smell (BSIT)				
	Vital Signs (BP)				

Participants will be contacted in between Visit 4 and Visit 5 to assess for adverse events. This contact will be considered Visit 4a.

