7.6 Visit 5 [Extended dosing; second week of product provision)

Visit 5 will occur 7 days after Visit 4. A safety assessment will be performed via medical interview and physical exam. An assessment of smell will be performed. The second week of study product will be provided. Participants will be provided with an administration log to record date and time of drug administration.

VISIT 5 FOLLOW-UP VISIT [week two of extended dosing]				
Component	Procedure/Analysis			
ADMINISTRATIVE	 Collect/Update Contact Information Visit Questionnaire Quality of Life Survey Update Medical History and Concomitant Medications Protocol Counseling Assess/Document Adverse Events Provision of Study Product (week two supply) Schedule Next Study Visit Participant Reimbursement 			
PHYSICAL EXAM	 Targeted Physical Exam Assessment of Smell (BSIT) Vital Signs (BP) 			
BLOOD	 CBC with platelets AST, ALT Creatinine Total Bilirubin 			

Table 5: Visit 5 Follow-up Visit Procedures

Participants will be contacted in between Visit 5 and Visit 6 to assess for adverse events. This contact will be considered visit 5a.

7.7 Visit 6

Visit 6 will occur approximately 13 days after Visit 4. Every effort will be made to time the study visit for 24 hours after the last self-administered dose. At this visit, a safety assessment will be performed via medical interview, targeted physical exam, and repeat blood tests. An assessment of participant smell will be performed using the BSIT. Blood and respiratory samples will be collected. An acceptability questionnaire will be administered. Participants have the option to have a rectal swab collected.

VISIT & FULLOW-UP VISIT [24 nours after last self-administered dose]				
Component	Procedure/Analysis			
ADMINISTRATIVE	 Collect/Update Contact Information Visit Questionnaire Quality of Life Survey Update Medical History and Concomitant Medications Protocol Counseling Assess/Document Adverse Events Schedule Next Study Visit Participant Reimbursement Q-GRFT level 			
BLOOD	 ADA test for Anti Q-GRFT antibodies CBC with platelets AST, ALT Creatinine Total Bilirubin 			
ACCEPTABILITY	Acceptability Questionnaire			
URINE	Pregnancy test (participants of childbearing potential)			
NASAL	Q-GRFT level			
OROPHARYNGEAL	Q-GRFT level			
NASOPHARYNGEAL	Q-GRFT level			
RECTAL (optional)	Q-GRFT level			
PHYSICAL EXAM	 Targeted Physical Exam Assessment of Smell (BSIT) Vital Signs (BP) 			

T	able	6:	Visit	6	Follow	-up	Visit	Ρ	rocedu	ires
		17							la a coma	- 44 -

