8.6 Criteria for Early Termination of Study Participation

Participants may voluntarily withdraw from the study for any reason at any time. The Site Pl/designee also may withdraw participants from the study to protect their safety and/or if they are unwilling or unable to comply with required study procedures. Participants also may be withdrawn if the study sponsors, government or regulatory authorities, including the Office of Human Research Protections (OHRP), or site IRBs/ECs terminate the study prior to its planned end date. Every reasonable effort is made to complete a final evaluation of participants who withdraw or are withdrawn from the study prior to completing follow-up. Study staff members will record the reason(s) for all withdrawals in participants' study records.

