10.6 Study Pause/Discontinuation

NCI or the University of Pittsburgh Institutional Review Board may discontinue this study at any time. Ongoing safety monitoring will track the incidence of AEs.

The study will be paused if the following should occur:

- Two or more Grade 3 AEs that are similar in nature and related to study product
- Any Grade 4 AE or SAE related to study product

If the study is paused, the Independent Safety Monitor will evaluate the safety data and recommend whether the study should be discontinued or may be continued with or without a protocol amendment.

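### Section 8.4 orders no product hold for a related, non-serious Grade 3 AE while its 5-day ENT review is pending, so up to 5 more daily home doses can be taken first, and late in the course all that remain

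*Combined protocol and SAP*

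**What the plan says.** Section 8.4 has two tiers for AEs judged related to product.

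- Grade 3: the event "will be reviewed within 5 days by an ENT investigator". Then: "The ENT investigator and the PI will determine whether the participant will continue in the study". Nothing is said about dosing between identification and that decision.
- Grade 4 or serious: for a related Grade 4 AE or "any SAE related to the study product, the study product will be held", with ENT review inside 3 days and discontinuation from the study.

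Four other sections bear on the point.

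- 7.5 sets a gate before the 13-day course. If a Visit 3 safety lab is Grade 2 or higher, "this visit will be postponed until the abnormal lab returns to Grade 1 or Grade 0", within the 49-day window.
- 7.6 covers Visit 5, on days 5-7 after Visit 4: "The second week of study product will be provided". Safety labs are drawn at the same visit. Afterwards, "Participants will be contacted in between Visit 5 and Visit 6 to assess for adverse events" (contact 5a).
- 8.6 says the site PI or designee "may withdraw participants from the study to protect their safety".
- 10.6 pauses the whole study for "Any Grade 4 AE or SAE related to study product", or for at least two similar related Grade 3 AEs.

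**The concern.** The ENT/PI review exists to decide whether a participant with a severe related event should go on. If dosing continues by default until then, the decision can arrive after some or all of the doses it was meant to govern. Section 8.4 writes a hold for one tier and omits it for the other, so a site following the text has no instruction to stop.

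The gap is confined to the 13-day course. After the single dose at Visit 2, the next dose comes at Visit 4, at least 5 days after Visit 3, and the 7.5 lab rule applies. No matching rule covers a Grade 3 lab from Visit 4 or Visit 5, or a Grade 3 symptom during daily dosing. Weekly dispensing limits exposure only until Visit 5, when the rest of the supply goes home.

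This is the first multi-day intranasal use in humans. Section 2.4 reports that the 15-day rabbit study found no intranasal NOAEL and saw lung findings scored minimal to mild, with only partial recovery in females. Continued self-dosing through a severe related event should be somebody's decision rather than the default.

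**Working it through.** **Inputs.** One clinic dose at Visit 2, then a 13-day course whose first dose is observed at Visit 4 (6.1, 7.5). Visit 5 on days 5-7, Visit 6 on day 13 or day 12, counted after Visit 4 (7.9). If Visit 6 is on day 12, the final home dose is not taken (7.9). Grade 3 review deadline: 5 days (8.4).

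**The plan's own figure.** 1 + 13 = 14 doses, as 6.1 states. With Visit 4 as day 0, the 13 doses fall on days 0-12, and Visit 6 on day 13 is 24 hours after the last.

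**Doses that can precede the deadline.** Take an event found on day *d*, after that day's dose. Review is due on day *d* + 5. Doses left = L - *d*, where L is the day of the last dose. Doses that can be taken through the due day = min(5, L - *d*). All remaining doses fall strictly before the due day when 0 < L - *d* < 5.

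| Day found | Review due | Doses left, Visit 6 on day 13 (L = 12) | Doses left, Visit 6 on day 12 (L = 11) |
|---|---|---|---|
| 6 | 11 | 6 | 5 (last on due day) |
| 7 | 12 | 5 (last on due day) | 4 |
| 8 | 13 | 4 | 3 |
| 9 | 14 | 3 | 2 |
| 10 | 15 | 2 | 1 |
| 11 | 16 | 1 | 0 |

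The condition holds on days 8-11 when L = 12 and on days 7-10 when L = 11. For earlier events the ceiling is 5 doses counting the due day (4 strictly before it), with some doses still left after the review.

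**Faster review.** Replacing 5 by the actual review time, a 3-day review allows at most 3 doses and a 1-day review at most 1.

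**Contact 5a.** If made mid-interval (an assumption; 7.6 gives no day), it falls between (5+13)/2 = 9 and (7+13)/2 = 10 with Visit 6 on day 13, and between (5+12)/2 = 8.5 and (7+12)/2 = 9.5 with Visit 6 on day 12. Both lie inside the matching range above.

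**Visit 5 labs.** Drawn on days 5-7; if results take 0-2 days (assumed), they are known on days 5-9. With L = 12, min(5, 12 - *d*) gives 5, 5, 5, 4, 3 doses, leaving 2, 1, 0, 0, 0.

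**How many a hold would touch.** The documents give no rate of related, non-serious Grade 3 AEs. At an assumed 1-3% in both arms: 45 × 0.01 = 0.45 to 45 × 0.03 = 1.35 participants.

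**The case against.** The strongest reply is that the tiers are a deliberate choice: prompt specialist review with clinical judgement for Grade 3, and a mandatory stop for Grade 4 and SAEs. Several safeguards support it.

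- Under 8.3 the Protocol chair or designee grades severity and relatedness, so a senior clinician already knows of the event when it is called related Grade 3. Section 8.6 lets the PI act.
- Participants are told how to report events (8.3), and interim visits are available (7.11).
- Product is released only on a signed prescription (6.5), and the second-week supply follows a safety assessment (7.6).
- The SAE definition in 8.3 includes important medical events that may jeopardize the participant, so the more dangerous Grade 3 events can already trigger the hold.

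All of this stands and it narrows the gap. It does not close it: for the non-serious remainder each safeguard depends on someone choosing to act.

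The contrast with the Visit 3 lab rule should also not be pressed. That rule is a one-time gate between single and repeat dosing and ignores relatedness; it is not a stopping standard for the course.

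A reader might infer that participants will in fact be dosed through severe events, or that the plan prevents investigators from stopping. The text supports neither: it is silent, five days is an upper limit, and discretion is explicit. Nor can one infer a probability that someone falls in the days 8-11 window by spreading an assumed rate evenly over the 13 dosing days. That treats day of onset as day of discovery. An event starting late may first be found at Visit 6, when a hold no longer helps, and an earlier one may surface at contact 5a.

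**Conclusion.** The point holds as a small gap in the safety rules, worth closing at the next amendment. For a related, non-serious Grade 3 AE found during the 13-day course, the plan requires no hold and permits up to 5 further doses by the review deadline. For events found on days 8-11 after Visit 4 (days 7-10 when Visit 6 is on day 12), all remaining doses can precede the due date, and the continuation decision then has no dosing left to govern.

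The dose counts assume daily dosing as scheduled, discovery after that day's dose, and a review that takes the full 5 days. They are ceilings. Grade 3 events that are also SAEs are outside the point because they already trigger the hold. Few participants are likely to be affected, but no reliable frequency can be drawn from the documents.

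**What to change.** Replace the Grade 3 text in 8.4, including its existing sentence on continuation so that two rules do not stand side by side, with:

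> For any Grade 3 AE (clinical or laboratory) deemed related to study product, study product is held, and further supply is not dispensed, from identification until the ENT investigator has reviewed the event (within 5 days) and the ENT investigator and PI decide whether dosing resumes. A Grade 3 laboratory value may be repeated at an interim visit during the hold. Missed doses are not made up. A participant who does not resume dosing stays in follow-up off product and keeps Visits 6 and 7.

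Report these participants as having received fewer than 14 doses in the safety summary as well as the persistence and PK summaries. They remain evaluable under 9.6.3 by completing Visit 6, while the primary objective concerns safety after 14 doses.

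The cost is a short text change and a reporting flag, with no new scheduled visits or changed windows, and no hold for Grade 2 or unrelated events. Because the study is blinded, the hold applies to both arms: about 0.5-1.4 of 45 participants at the assumed 1-3% rate. Those held may give no true 13-consecutive-dose sample. With Visit 6 on day 13, a hold starting on days 8-11 in effect ends dosing if the review takes the full 5 days. A 1-day review of an event found on day 8 would still leave 12 - 8 - 1 = 3 doses.

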7.10 Participants Who Become Pregnant

Urine pregnancy tests will be performed at screening, enrollment Visit 4, Visit 6, and Visit 7 for participants of pregnancy potential. Participants who become pregnant will be referred for care. Participants will remain in the study for safety but study product will be discontinued, if applicable . Pregnant participants will be contacted after their study participation to ascertain the pregnancy outcome.

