7.11 Interim Visits

Interim visits may be performed at any time during the study (and study procedures repeated as clinically indicated), for the following or other reasons:

• In between screening and enrollment or Visits 3 and 4 if laboratory tests need to be repeated due to out of range values

- For administrative reasons, e.g., a participant may have questions for study staff, or may need to re-schedule a follow-up visit.
- In response to AEs. When interim contacts or visits are completed in response to participant reports of AEs, study staff will assess the reported event clinically and provide or refer the participant to appropriate medical care.
- In the event of laboratory processing issues (i.e., lost or inadequate sample)
- For other reasons at participant request.

Details of the interim visit will be recorded in the chart notes.

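### Section 8.4 ties coming off product after a serious related reaction to leaving the study, and nothing secures the remaining safety assessments and post-dose antibody samples

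*Combined protocol and SAP*

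**What the plan says.** Section 8.4 sets two rules for events related to study product.

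- **Grade 3:** an ENT investigator reviews the event within 5 days, and then "The ENT investigator and the PI will determine whether the participant will continue in the study".
- **Grade 4, or any SAE:** "the study product will be held", ENT review follows within 3 days, and the text ends: "They will be discontinued from the study and followed for safety and outcome of the event". This last step does not depend on what the review finds.

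For pregnancy, section 7.10 separates the two acts: "Participants will remain in the study for safety but study product will be discontinued, if applicable". Section 10.1 adds that these participants carry on with their follow-up visits.

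Four other provisions bear on what is collected after removal:

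- Section 8.6: "Every reasonable effort is made to complete a final evaluation of participants who withdraw or are withdrawn from the study". The content of that evaluation is not defined.
- Section 8.3: clinically significant events are followed until they resolve or are stable over four weeks. SAEs still open at exit are re-assessed at least 2 weeks later.
- Section 7.11: interim visits prompted by an AE are allowed, with procedures repeated where there is a clinical reason.
- Section 8.3 again: all AEs go on the AE log.

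ADA is listed in Table 2 (Visit 2, before dosing), Table 6 (Visit 6) and Table 7 (Visit 7). It is not listed in Tables 3, 4 or 5.

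**The concern.** In a first multi-day intranasal study, a participant with a serious related reaction is the one whose later results are most informative. Section 2.4 describes Q-GRFT as immunogenic though not immunotoxic and reports antibodies in 11 rabbits after intranasal or intravenous dosing. Section 10.2 names anaphylaxis as a rare risk. Whether such a participant developed antibodies, and whether labs and the nose and throat exam returned to baseline, are questions the team would want answered.

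Section 8.4 makes the reaction itself the reason for leaving the visit schedule on which those results are collected. The missing values would then be missing because of the reaction, and the ADA summary would lean towards people who tolerated the product. The protocol already uses the alternative, off product but still followed, for pregnancy. It does not offer it in writing for a related reaction.

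**Working it through.** The plan states no figure on this point, so the check sets its provisions side by side and adds a little arithmetic.

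**1. What is still outstanding when a participant is removed.** Inputs: the visit tables in sections 7.3 to 7.8 and the windows in section 7.9. Dose 1 is given at Visit 2. Doses 2 to 14 start at Visit 4, and the last is timed about a day before Visit 6.

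| Removal occurs | Scheduled safety labs and exam outstanding | Post-dose ADA outstanding |
|---|---|---|
| After the Visit 2 dose, before Visit 4 | Visit 3 (if not yet done) and Visits 4, 5, 6, 7 | 2 of 2 |
| Between Visits 4 and 5 | Visits 5, 6, 7 | 2 of 2 |
| Between Visits 5 and 6 | Visits 6, 7 | 2 of 2 |
| Between Visits 6 and 7 | Visit 7 | 1 of 2 |

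All 14 doses precede Visit 6. A reaction leading to removal during dosing therefore comes while both post-dose ADA samples are still to be taken.

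**2. Whether another provision secures those items.**

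| Provision | Secures scheduled labs and exam? | Secures ADA? |
|---|---|---|
| 8.4, follow-up for safety and event outcome | Not stated | Not stated |
| 8.6, final evaluation, best effort | Content undefined | Content undefined |
| 8.3, re-assessment of the event | Only as the event requires | Not stated |
| 7.11, interim visits | Only where clinically indicated | Not stated |
| 7.10 and 10.1, pregnancy only | Follow-up visits continue | Follow-up visits continue |

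**3. How many participants.** One participant is 1/30 = 3.3% of the Q-GRFT arm (30 planned, section 9.2). The documents give no rate of related Grade 4 events or SAEs, so the rates p below are assumptions. The chance of at least one among 30 is 1 − (1 − p)^30:

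- p = 1%: 1 − 0.99^30 = 26.0%
- p = 2%: 1 − 0.98^30 = 45.5%
- p = 5%: 1 − 0.95^30 = 78.5%

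**4. What continued follow-up can recover.** ADA, safety labs and the exam can be collected whether or not product continues. The repeat-dose concentration endpoints and the smell endpoint (9.3.2, 9.3.3) cannot be met, because they are defined after 13 consecutive daily doses. A late plasma level would also say little about exposure at the time of the reaction. Taking the rabbit intranasal half-lives in section 2.5 (15.8 to 18.8 h) and assuming seven days (168 h) off product, the fraction remaining is 2^(−168/15.8) = 0.06% to 2^(−168/18.8) = 0.2%.

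**The case against.** The best defence is that 8.4 does not discard anyone. Product is held as well, so removal from the study is not a substitute for stopping product. Follow-up covers safety and not only the event. Section 8.6 aims for a final evaluation, and 8.3 requires re-assessment of open SAEs. All of this stands. It shows that the gap is one of undefined content, but it does not fill the gap: none of these provisions names ADA or the scheduled labs.

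A reader might infer several stronger things that the documents do not support:

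- **That Visit 6 and 7 data are lost by rule.** They are unsecured. A final evaluation could include them, and after Visit 6 only Visit 7 is at stake.
- **That Grade 3 participants must leave.** The decision is case by case, and continuing in the study does not exclude continuing without product. The text simply does not say so.
- **That the hold and the ENT review have no effect.** Hold, review, then discontinue is a workable sequence, and the review may inform grade or relatedness. How a hold on product relates to discontinuation from the study still needs to be stated.
- **That the concentration and smell summaries are biased in a way continued follow-up would cure.** Early stoppers cannot supply those endpoints.
- **That the Safety Monitor's pause review under 10.6 would be deprived of these data.** Visits 6 and 7 fall about 13 and 28 days after Visit 4. For an early event, their results would not exist when the review began.
- **That the primary-endpoint event disappears.** It is on the AE log. It would drop out only if safety were analysed in the evaluable cohort, which requires Visit 6 (9.6.3). The plan does not name a cohort for the primary analysis, and that is a separate question.

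**Conclusion.** The point holds in a limited form. Section 8.4 couples stopping product with leaving the study after a related Grade 4 event or SAE, and writes no option to stop product and stay for a related Grade 3 event. The protocol applies that option to pregnancy. As written, a participant removed before Visit 6 may have none of the two scheduled post-dose ADA samples and an undefined set of recovery labs and exams; one removed after Visit 6 risks one ADA sample and one set.

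The number affected is probably small, and the probabilities above rest on assumed rates. The primary endpoint is not damaged by 8.4 itself. The loss is in the completeness of safety follow-up and of an exploratory immunogenicity endpoint, in the few participants for whom those data would matter most. The ADA part rests on the legible visit tables, because the ADA row of the Appendix 1 schedule cannot be read reliably in the text available.

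**What to change.** Reconcile sections 8.4, 7.10 and 8.6 as follows.

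1. State discontinuation of product and discontinuation from study follow-up as separate decisions. The product decision, including how holding relates to discontinuing, is for the clinicians to settle; none is proposed here.
2. State that participants taken off product because of an AE are asked, unless they withdraw consent, to complete the remaining scheduled safety assessments (labs, nose and throat exam) and ADA sampling through Visit 7.
3. For an event before Visit 4, anchor the timing to the last dose. Visits 5 to 7 are otherwise counted from a Visit 4 dosing start that will not take place.
4. Report any Q-GRFT concentrations and BSIT scores from these participants descriptively, apart from the endpoint summaries, because they do not meet the endpoint definitions.

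This is a wording amendment, submitted to the IRB under section 12.4. The visits and assays are already scheduled for every participant. The downside is visit burden for someone who has stopped product.
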